9.1.3.5 Potential risks to patients

The majority of these analyses will involve archival tissue previously obtained through clinical procedures performed as part of routine clinical care. As such, no additional risks will be posed for patients. In the situation where no archival tissue exists, or if archival tissue is not suitable for analysis (e.g. does not contain tumor tissue), then tissue for analysis will be obtained from the protocol related pre-treatment biopsy outlined above in Section 9.1.1. The risks associated with these biopsies are outlined in Section 9.1.1. However, since patients will already be undergoing these biopsies as part of the research study plan, no additional risk will be posed by utilizing the tissue that is collected for these analyses.

9.1.4 Blood collection for cell-free circulating tumor DNA (cfDNA) analysis

9.1.4.1 Rationale

cfDNA analysis represents an increasingly important and noninvasive means of assessing mutations in tumor-derived DNA shed into the bloodstream by tumor cells throughout the patient's body. cfDNA analysis can provide a highly specific means of monitoring tumor burden by tracking the abundance of tumor-derived DNA mutations in the blood throughout treatment. Sequencing of cfDNA can also provide a non-invasive means of performing targeted or comprehensive tumor mutational analysis without the need for a biopsy.

9.1.4.2 Procedures and analyses

20 mL of peripheral blood will be collected in two 10 mL Streck cfDNA tubes at each of the timepoints outlined in the study calendar, including pre-treatment, at various intervals during treatment and at disease progression. Streck tubes containing whole blood can be shipped at room temperature (within 5 days of draw) to:

[name] Laboratory Massachusetts General Hospital Cancer Center [name]

Cell free plasma will be isolated through two serial centrifugations steps, and plasma and blood cell pellet will be aliquoted and frozen. cfDNA will be isolated from 5 mL using a QIAGEN cfDNA kit and will be analyzed by droplet digital PCR (ddPCR) using probes specific to the particular KRAS or NRAS mutation present in each patient's tumor. Serial measurement of KRAS or NRAS mutational abundance in cfDNA throughout treatment will provide a non-invasive and personalized means of monitoring tumor burden, and the change in mutation levels in cfDNA will be correlated with radiographic response. In select patients of interest, such as patients who respond to therapy, but ultimately progress, cfDNA derived from pre-treatment and post-progression plasma may be analyzed by next-generation sequencing methods to identify potential mechanisms of acquired resistance.

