2.5.3.1 Mutational Analysis

Extensive tumor mutational analysis of 1000 genes will be performed for each patient using a next-generation genotyping platform employed as part of standard oncology care at the Massachusetts General Hospital Cancer Center. Mutations in key pathways that might affect the likelihood of a patient's tumor to respond to therapy (e.g. PIK3CA, PTEN, p53, etc.) will be correlated with objective tumor response or PFS. Additional in-depth genomic analyses, including copy number analyses, may also be performed.

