2.5.3.2 Biomarker Expression Analysis

We also plan analysis of selected protein and mRNA biomarkers identified in previous (and future) laboratory studies. For example, our initial laboratory studies ([name] et al., Cancer Cell, 2013) have suggested that KRAS mutant cancers that express markers of epithelial differentiation (e.g. E-cadherin) are more likely to respond to this therapy that cancers expressing markers of mesenchymal differentiation (e.g. vimentin). Thus, E-cadherin and vimentin levels will be assessed by immunohistochemistry in archived or pre-treatment biopsies. Also, baseline levels of specific BCL2 family apoptotic proteins, including BCL-XL, MCL1, and BIM, have also been shown to predict responsiveness to this therapy in laboratory models. These markers will also be assessed. Biomarker levels will be correlated with response rate or PFS and may help identify which subpopulation of KRAS or NRAS mutant cancer patients are more or less likely to response therapy.

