9.1.3 Identification of potential predictive biomarkers in pre-treatment tumor tissue

9.1.3.1 Rationale

Given the molecular heterogeneity of KRAS and NRAS mutant cancers, no single therapeutic regimen is expected to be effective in all patients. Therefore, molecular characterization of archived or pre-treatment tumor biopsy tissue for each patient enrolled on this trial will provide a critical opportunity to identify valuable biomarkers to predict which patients are more or less likely to respond to treatment. Initially, these analyses will be exploratory and hypothesisgenerating in nature, but promising biomarker candidates identified in this study can potentially be assessed in future clinical studies evaluating this therapeutic regimen.

Initial laboratory studies evaluating the combination of BCL-XL and MEK inhibition in KRAS mutant cancer cell lines have identified potential biomarkers of sensitivity. For example, our initial studies ([name] et al., 2013) have suggested that KRAS mutant cancers that express markers of epithelial differentiation (e.g. E-cadherin) are more likely to respond to this therapy than cancers expressing markers of mesenchymal differentiation (e.g. vimentin). Thus, E-cadherin and vimentin levels will be assessed by immunohistochemistry in pre-treatment tumor tissues of all patients enrolled on this study and correlated with clinical outcome. Our initial

Version Date: July 22, 2022

work has shown that E-cadherin and vimentin can be readily assessed in formalin-fixed paraffinembedded tissue from KRAS mutant cancer patients ([name] et al, 2013).

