9.1.3.3 Mutational analysis

In depth, mutational analysis will be performed using a 1000 gene next-generation sequencing platform employed as part of standard oncology care at the Massachusetts General Hospital Cancer Center. Mutations in these 1000 cancer-related genes that might affect the likelihood of a patient's tumor to respond to therapy will be correlated with clinical outcome. In addition, further in-depth genomic analyses, including copy number analysis, may be performed on selected specimens.

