Target lesions. All measurable lesions up to a maximum of 2 lesions per organ and 5 lesions in total, representative of all involved organs, should be identified as **target lesions** and recorded and measured at baseline. Target lesions should be selected on the basis of their size (lesions with the longest diameter), be representative of all involved organs, but in addition should be those that lend themselves to reproducible repeated measurements. It may be the case that, on occasion, the largest lesion does not lend itself to reproducible measurement in which circumstance the next largest lesion which can be measured reproducibly should be selected. A sum of the diameters (longest for non-nodal lesions, short axis for nodal lesions) for all target lesions will be calculated and reported as the baseline sum diameters. If lymph nodes are to be included in the sum, then only the short axis is added into the sum. The baseline sum diameters will be used as reference to further characterize any objective tumor regression in the measurable dimension of the disease.

Non-target lesions. All other lesions (or sites of disease) including any measurable lesions over and above the 5 target lesions should be identified as **non-target lesions** and should also be recorded at baseline. Measurements of these lesions are not required, but

the presence, absence, or in rare cases unequivocal progression of each should be noted throughout follow-up.

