The primary goal of Part 2 is to evaluate the efficacy of this regimen in patients with various KRAS or NRAS mutation-positive solid tumor. Based on traditional response rates to standard second line chemotherapy in the tumor types being studied (Guglielmi et al, 2007; Conroy et al, 2011), we conclude that a response rate of 15-20% or greater in a given expansion cohort would deem this regimen worthy of further study in that specific patient population. In part 2, patients will be enrolled in 4 expansion cohorts by a two-stage design, as outlined in Section 5.1. Initially 12 patients will be enrolled to each cohort in Stage 1. If no responses are observed in a given cohort among the first 12 patients, then that cohort will be stopped for futility. However, if one or more responses are observed in a given cohort, the cohort will proceed to Stage 2, and an additional 13 patients will be enrolled for a total of 25 patients in that cohort. If at least three responses are observed within a completed cohort of 25 patients, the regimen will be considered promising for treating the specific tumor type. This design has a 11% false-positive and a 22% false-negative error rate for testing a 17% vs. a 5% response rate. The probability of early stopping is 54% if the underlying response rate were truly only 5%. In the event that the number of responses observed in a given cohort does not meet the pre-established response criteria defined above, but promising anti-tumor activity is observed (such as prolonged stable disease or tumor regressions that fall short of the RECIST cutoff for partial response), the possibility of further evaluating of this regimen in the specific patient population can be explored through a joint discussion between the investigators, pharmaceutical collaborators, and the NCI-CTEP.

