13.1.2.2 Primary Endpoints

- Response rate (partial response [PR] + complete response [CR])
- Progression-free survival (PFS)
- Adverse events

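### The exploratory tissue-marker, mutation and cfDNA correlations do not name percent change in tumour size as an outcome, although the trial records it and a responder/non-responder split would keep only about 22-45% of its information

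*Combined protocol and SAP*

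**What the plan says.** **cfDNA (9.1.4.2).** Serial mutant-allele abundance is presented as a way to follow tumour burden, and "the change in mutation levels in cfDNA will be correlated with radiographic response". No scale, test or time point is given for the response variable.

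**Tissue markers and mutations.** Section 2.5.3.1 says that mutations in key pathways "will be correlated with objective tumor response or PFS". Section 2.5.3.2 says "Biomarker levels will be correlated with response rate or PFS". Section 9.1.3.3 is looser: mutations that "might affect the likelihood of a patient's tumor to respond to therapy will be correlated with clinical outcome". Section 5.1.2 defines an objective response as partial or complete, and Section 13.1.2.2 defines response rate as PR plus CR.

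**What is measured.** Section 11.1 sets re-evaluation every 8 weeks. Section 11.1.2 records the baseline sum of target-lesion diameters and adds: "The baseline sum diameters will be used as reference to further characterize any objective tumor regression in the measurable dimension of the disease". Section 11.1.4.1 sets PR at a 30% or greater fall in that sum.

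**Status.** Section 9.1.3.1 says of the predictive-biomarker work: "Initially, these analyses will be exploratory and hypothesisgenerating in nature". Section 13 gives no test, alpha, effect size or sample size for the tissue-marker, mutation or cfDNA correlations.

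**The concern.** Percent change in the sum of diameters can be derived for every patient with a post-baseline scan, at no extra cost, yet it is not named as an outcome for any of these correlations. The tissue-marker sections name a two-level outcome with few patients on one side: the design works with response rates of 5% and 17%. A PR+CR split puts a patient with 29% shrinkage in the same group as one with 19% growth. Section 13.1.2 itself counts "tumor regressions that fall short of the RECIST cutoff for partial response" as possible evidence of promising activity, and a responder/non-responder outcome discards exactly that.

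For cfDNA, the stated purpose is to follow tumour burden, which is continuous. The Schedule C calendars in Section 10 place a draw on day 1 of each cycle. Two 28-day cycles make 56 days, so a draw falls close to each 8-week scan and the two series can be paired.

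At stake is whether these analyses can pick out markers that track tumour shrinkage, and whether they can show that cfDNA tracks tumour burden. No go/no-go decision depends on them.

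**Working it through.** **1. The plan's own design, reproduced.** Inputs from 13.1.2: 12 patients in stage 1, stop if there are no responses; otherwise 13 more, promising if at least 3 of 25 respond; 5% versus 17%.

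- Early stopping at 5%: (1 − 0.05)^12 = 0.540 (stated 54%).
- P(promising) = Σ over x ≥ 1 of b(x; 12, p) × P[Bin(13, p) ≥ 3 − x]. At 5% this is 0.114 (stated 11%). At 17% it is 0.781, so the miss rate is 0.219 (stated 22%).

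The stated figures are right, and 5% and 17% are the relevant response rates.

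**2. Information kept by a responder/non-responder split.** Assume that marker and percent change are bivariate normal and that responders are the lowest fraction p of changes. The correlation shrinks by φ(z_p)/√[p(1 − p)], and the relative efficiency is the square of that factor.

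| Response rate p | Correlation multiplied by | Information kept | Information lost |
|---|---|---|---|
| 5% | 0.473 | 22.4% | 77.6% |
| 17% | 0.674 | 45.4% | 54.6% |

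**3. From information to power.** This needs a correlation, which the documents do not give, and an alpha (two-sided 0.05 assumed). By the Fisher transformation, power ≈ Φ(atanh(r)·√(n − 3) − 1.96). Take n=100, the Part 2 maximum in 13.2.2, and correlation 0.3:

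- continuous: atanh(0.3) = 0.3095; × √97 = 3.05; power 86%
- split at 5%: r = 0.3 × 0.473 = 0.142; 0.143 × √97 = 1.41; power 29%
- split at 17%: r = 0.3 × 0.674 = 0.202; 0.205 × √97 = 2.02; power 52%

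Simulated power, Pearson correlation on the full scale against point-biserial on the split (20,000 runs per cell):

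| n | Correlation | Continuous | Split at 5% | Split at 17% |
|---|---|---|---|---|
| 48 | 0.3 | 55-56% | 15% | 29% |
| 48 | 0.4 | 82% | 24% | 46% |
| 100 | 0.3 | 86-87% | 29% | 53% |
| 100 | 0.5 | >99% | 64% | 94% |

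Rank methods (Spearman against Mann-Whitney) at correlation 0.3 give 81-82% against 27% and 50% at n=100, and 50% against 14% and 26% at n=48.

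**4. If response means ordered PR/SD/PD.** With 30-50% of patients assumed to have PD, optimally scored ordered categories keep about 73-80% of the information. At n=100 and correlation 0.3, with 40% PD assumed, the power loss is about 8-12 points.

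**The case against.** The other side has real force on five points.

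- **The cfDNA outcome is open.** A reader might infer that the plan has chosen the RECIST responder category for cfDNA. Section 9.1.4.2 does not say so; its wording fits percent change or ordered categories as well. This stands: for cfDNA the defect is an unstated scale, not a wrong choice.
- **PFS is already an alternative for tissue markers**, and 9.1.3.3 refers only to clinical outcome. This stands in part. PFS does not depend on the −30% cut, but in a single-arm study it mixes prognosis with drug effect, and it is not offered for cfDNA.
- **RECIST response is more than a cut at −30%.** Section 11.1.4.3 also takes account of non-target and new lesions and requires confirmation at 4 weeks or more. The efficiencies above therefore describe an idealised version. Target-lesion change also follows at most five lesions, two per organ, whereas cfDNA reflects disease throughout the body. This is why the fix needs a rule for new and non-target progression and keeps RECIST response alongside.
- **The analysis set is not stated.** A reader might infer that a cohort closed after 12 patients contributes nothing because it has no responders. That is so only for a within-cohort comparison, and the plan does not stratify these correlations by cohort. The 21-30 Part 1 patients may contribute tissue-marker data too, and the figures above leave them out.
- **The work is exploratory.** Neither cfDNA nor the predictive markers appear among the objectives in Section 1 or the endpoints in Section 13. This limits the importance of the point but does not remove it: analyses with few responders gain most from using the full scale.

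**Conclusion.** The point holds as a low-cost improvement to exploratory analyses. Objective response or PFS is named for mutations and expression markers, and an unscaled radiographic response for cfDNA; the continuous measure the trial already records is not named for any of them. A PR+CR split at 5-17% keeps about 22-45% of the information in that measure, assuming bivariate normality and a linear association.

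A reader might infer that the analyses lose half or more of their power. The documents do not support that as a general statement. At the 17% rate with correlation 0.3, the rank-based falls from 82% to 50% (n=100) and from 50% to 26% (n=48) are relative losses of 39% and 48%. At n=100 and correlation 0.5 the relative loss is about 36% at a 5% rate and about 6% at 17%. With ordered categories it is smaller than under the split. The size therefore turns on n, on the scale chosen and on a correlation that is assumed throughout. No figure in the plan is wrong, and the primary analysis is untouched.

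**What to change.** In 2.5.3.1, 2.5.3.2, 9.1.3.3 and 9.1.4.2, add percent change from baseline in the sum of target-lesion diameters as the main outcome for these correlations:

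- **Baseline tissue markers and mutations:** best percent change; rank correlation for marker levels, a rank test for mutation present versus absent.
- **cfDNA:** percent change at the scan that matches the draw; rank correlation.
- **Worst rank** for patients who die or progress before any post-baseline measurement, and for patients whose progression is by new lesions or unequivocal non-target progression at the scan used (for best change, at the first post-baseline scan). Without the second part, a patient with shrinking target lesions and new metastases would rank as a good outcome.
- **Supportive outcomes:** RECIST response for all these analyses, with its scale stated, and PFS for the tissue markers and mutations.

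Leave the primary endpoint and the 12/25-patient decision rules as they are.

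The cost is a wording change and slightly more analysis, with no extra scans, blood draws or patients. The remaining weakness is that target-lesion change does not itself reflect new or non-target disease, which the worst-rank rule and the supportive RECIST analysis are there to cover.

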9.1.4.3 Risks to patients

All blood for cfDNA analysis will be drawn at the time of routine lab draws for other study-associated blood draws, and thus will not pose significant additional risk to the patient.

9.2 Investigational Device Information

N/A

9.3 Laboratory Correlative Studies

9.3.1.1 Pharmacokinetic Studies of navitoclax and trametinib dosed in combination

While the pharmacokinetics (PK) of trametinib and navitoclax given as single agents is well-understood, this study will evaluate the pharmacokinetics of these agents when given in combination. These studies will be used to determine whether trametinib and navitoclax interact from a pharmacokinetic standpoint, and will be used to determine the plasma drug exposures achievable at a particular combination dose level and at the maximally-tolerated dose and RP2D. The pharmacokinetics and plasma drug levels achieved during combination dosing will have key implications on the potential for efficacy at a given dose level.

During Part 1 (the Phase 1b portion) of the study, subjects will have blood drawn pre-dose (0h), and 2h, 4h, 6h, 8h, and 23h after dosing of navitoclax on (1) day 7 of a 7-day navitoclax single-agent lead-in dosing period and (2) again after 14 days of combination dosing. The exact timing of PK blood draws will thus vary depending on whether navitoclax is being given as a single-agent and whether a subject is following dosing schedule A or B/C (as defined in Section 5.1). The exact timing of PK draws are outlined in table format in section 9.3.1.2 below. Subjects will also have PK blood samples drawn pre-dose on day 1 of cycles 2, 4, 8, and 12.

During Part 2 (the Phase 2 portion) of the study, subjects will have PK blood samples drawn predose on day 1 of cycles 2, 4, 8, and 12. The exact timing of PK draws are outlined in table format in section 9.3.1.2 below.

PK blood samples will be analyzed by AbbVie (for navitoclax) and GSK (for trametinib) according to established procedures, and assessed for the endpoints described in Sections 2.5.1 and 13.4.1.1.

9.3.1.2 Collection of Specimens

PK blood specimens will be drawn according to the schedules below, which vary depending on which study part—Part 1 (Phase 1b) vs. Part 2 (Phase 2)—and which dosing schedule—Schedule A vs. B—to which a given subject has been enrolled.

For the purposes of these dosing schedules:

- (1) All blood draw times are relative to administration of navitoclax (0h = pre-dose for navitoclax).
- (2) On PK days, trametinib is to be dosed in the morning on empty stomach ONE HOUR (+/- 5 minutes) before navitoclax dose is administered with food. Thus, when a patient is receiving both drugs, an additional trametinib pre-dose (-1h) PK sample will be drawn.
- (3) On non-PK days, the medications do not necessarily need to be taken in this sequence, but trametinib should always be taken on an empty stomach (defined as at least one hour +/- 5 minutes before and/or two hours after food,) and navitoclax should always be taken with food. However, patients are encouraged to keep to the same schedule used on PK

days as part of their daily administration, if possible.

Procedures for sample collection are outlined in detail in APPENDIX C.

9.3.1.2.1 Schedule for PK sample collection for Part 1 (Phase 1b) Schedule A

Cycle (C), day (D)	Timing of PK sample blood draws	PK for
C1, D7*	Pre-dose (0h **,) 2h (+/-5 min,) 4h (+/-	Navitoclax only
	5min,) 6h (+/- 5 min,) 8h (+/-24 min)	
C1, D8*	Pre-dose trametinib (will represent 23h	Navitoclax only
	post dose navitoclax from prior day, +/-1	
	hr)	
C1, D21#	Pre-dose trametinib** (-1h), pre-dose	Navitoclax and
	navitoclax (0h**,) 2h (+/-5min,) 4h (+/-	trametinib
	5min,) 6h (+/-5min,) 8h (+/-24 min)	
C1, D22#	Pre-dose trametinib** (-1h)	Navitoclax and
	(will represent 23 h post-dose navitoclax	trametinib
	from prior day, +/-1hr)	
C2, D1	Pre-dose trametinib** (single trough	Navitoclax and
	level)	trametinib
C4, D1	Pre-dose trametinib** (single trough	Navitoclax and
	level)	trametinib
C8, D1	Pre-dose trametinib** (single trough	Navitoclax and
	level)	trametinib
C12, D1	Pre-dose trametinib** (single trough	Navitoclax and
	level)	trametinib

^{*} Navitoclax dosed as single-agent for 7-day lead-in under Schedule A. Thus, these PK assessments will be for navitoclax only. All other PK assessments will be for navitoclax and trametinib.

9.3.1.2.2 Schedule for PK sample collection for Part 1 (Phase 1b) Schedule B

Cycle (C), day (D)	Timing of PK sample blood draws	PK for
C1, D7	Pre-dose trametinib (-1h)**, pre-dose	Navitoclax and
	navitoclax (0h)**, 2h (+/-5 min,) 4h	trametinib
	(+/-5min,) 6h (+/-5 min,) 8h (+/-24	
	min)	
C1, D8	Pre-dose trametinib – (will represent	Navitoclax and
	23h post-dose navitoclax from prior	trametinib
	day, +/- 1 hr)	

[#]Represents 14th day of trametinib dosing under Schedule A

^{**} Pre- dose samples should be drawn within 5 minutes of dosing

C1, D14#	Pre-dose trametinib (-1h)**, pre-dose navitoclax (0h)**, 2h (+/- 5 min,) 4h (+/-5 min,) 6h (+/- 5 min,) 8h (+/- 24 min)	Navitoclax and trametinib
C1, D15#	Pre-dose trametinib (-1h)	Navitoclax and
	(will represent 23h post-dose navitoclax	trametinib
	from prior day, +/- 1 hr)	
C2, D1	Pre-dose trametinib** (single trough	Navitoclax and
	level)	trametinib
C4, D1	Pre-dose trametinib** (single trough	Navitoclax and
	level)	trametinib
C8, D1	Pre-dose trametinib** (single trough	Navitoclax and
	level)	trametinib
C12, D1	Pre-dose trametinib** (single trough	Navitoclax and
	level)	trametinib

^{**} Pre- dose samples should be drawn within 5 minutes of dosing *Represents 14th day of trametinib dosing under Schedule B

